Prior to testing, participants will complete the STAXI-2 online. Only individuals that meet the high/low trait anger inclusion criteria will be invited to participate. On arrival at the first session, participants will be given the opportunity to read the information sheet again and ask questions, before providing written informed consent. The researcher will conduct a short screening procedure to verify eligibility, which includes taking measures of weight and breath alcohol concentration (BrAC) (only participants with a BrAC of zero will be enrolled). Study documentation from failed screenings will be destroyed using the School's confidential waste facility. If eligible, participants will complete questionnaire measures (AUDIT, PANAS, BAES, S-Ang).

Participants will attend two sessions (order counterbalanced): at one session they will consume an alcoholic drink and at the other they will consume a matched placebo drink (see Drug Administration section for more details). Testing sessions will be held at least one week apart. Participants will be given 10 minutes to consume all of their drink and a further 10 minutes to sit quietly to allow for absorption. After drink consumption, participants will complete the 6AFC and 2AFC tasks. They will then complete questionnaire measures (PANAS, BAES, S-Ang), and a BrAC reading. Before leaving the session, participants will be required to read and sign a safety card, be offered the opportunity to stay behind until they feel any effects of alcohol have worn off and be offered a taxi home. At the end of session two, participants will be debriefed and reimbursed.

Table 1: Testing procedure timeline

Time (min)	Activity/Task
0	Informed consent and screening (session one only)
10	Questionnaire measures (AUDIT, PANAS, BAES, S-Ang)
20	Drink administration
30	Alcohol absorption period
40	Computerised tasks
65	Questionnaire measures (PANAS, BAES, S-Ang), BrAC reading
75	Debrief and reimbursement (session two only).

Drug Administration

The alcoholic drink will be 0.4 g/kg alcohol (vodka) with one part vodka and three parts tonic water. The placebo drink will comprise the same volume of tonic. Drinks will be flavoured with lime cordial and chilled prior to serving. The rim of the glass will be sprayed with a vodka mist. Drinks will be served double blind and will be made at the start of each session by a research collaborator.

Statistical Plan

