Ethics approval has been obtained from the Faculty of Science Research Ethics Committee at the University of Bristol (approval code: 26011747361). The study will be conducted according to the revised Declaration of Helsinki (2013) and the 1996 ICH Guidelines for Good Clinical Practice E6(R1). The investigator will explain the nature, purpose and risks of the study to the participant. The participant will receive the information sheet in advance of the study session. There will be no time restriction on how long participants take to respond, with the exception that participants who respond after all study places have been filled will not be offered a place on the study. Therefore, participants will be given sufficient time to read the information, consider any implications, and raise any questions with the investigators prior to making a decision to participate. On arrival at the study session participants will be given the opportunity to read the information sheet again and ask the investigator questions. Written consent will then be obtained. Participants will be informed that they are free to withdraw at any time.

Safety

Participants will be administered alcohol during one of the sessions. The dose will be 0.4 g/kg of body weight up to 90 kg. Participants weighing more than 90 kg will receive a dose based on 90 kg. This dosing will administer drinks ranging between around 2.5 to 4.5 units of alcohol (for weight ranges between 50-90 kg). We expect that at this dose, participants will feel some effects of alcohol but we do not expect high levels of intoxication (all participants will be weekly alcohol consumers). However, to ensure the safety of our participants, they will know in advance of the study that they may receive this dose of alcohol, and therefore will be able to make any necessary arrangements. They will be advised that should stay behind until they feel the effects of alcohol have worn off and they shouldn't drive, operate heavy machinery or do anything that would be considered unsafe after drinking alcohol for the rest of the day. Participants who have received alcohol will be asked to read and sign a post-study safety form to confirm that they understand these risks. We have standard operating procedures in place for adverse effects of alcohol (i.e., nausea, intoxication) and have facilities for people to stay behind until they feel ready to leave. Participants will be offered a local taxi at the end of the session.

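### The Safety section ties signing of the safety form to having received alcohol, which conflicts with the Procedure and, if applied after session one, would reveal the session-two drink

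*Protocol*

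**What the plan says.** Two sections of the protocol describe the safety document.

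- **Procedure:** "Before leaving the session, participants will be required to read and sign a safety card". No condition on the drink is attached.
- **Safety:** "Participants who have received alcohol will be asked to read and sign a post-study safety form". The risks it covers include a warning not to "do anything that would be considered unsafe after drinking alcohol for the rest of the day".

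On blinding, Drug Administration says "Drinks will be served double blind and will be made at the start of each session by a research collaborator". Each participant has one alcohol session and one placebo session, at least a week apart, and the debrief comes only at the end of session two. The blind is therefore evidently meant to last until then. On what participants are told, Safety says only that "they will know in advance of the study that they may receive this dose of alcohol".

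On breath alcohol, the Procedure describes what follows the computerised tasks: "They will then complete questionnaire measures (PANAS, BAES, S-Ang), and a BrAC reading". Table 1 puts this at minute 65. At screening, "only participants with a BrAC of zero will be enrolled", and Drug Administration says "The placebo drink will comprise the same volume of tonic". The protocol does not say who takes the minute-65 reading, who sees it, or whether it is hidden.

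**The concern.** A signature requested only from people who drank alcohol discloses the drink. In a parallel-group study, disclosure after the last assessment would do no harm. Here there is a second session still to come, and its drink is the complement of the first.

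What is at stake is the blinding of the session-two tasks and questionnaires. H1 to H5 all compare alcohol with placebo within person, so every participant's difference contains one session-two score. The tasks ask for judgements of briefly shown, often ambiguous faces, and the questionnaires are self-reports. Expectancy could act on either.

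The BrAC reading is a second possible route. Participants enter at zero and the placebo contains no vodka apart from the mist on the glass rim, so a clearly positive value at minute 65 of session one would identify alcohol to anyone who saw it.

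**Working it through.** The protocol gives no figure on this point, so there is none to reproduce. The check is to list the two drink orders under each reading of the signing rule.

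**Inputs.** There are 88 participants with two sessions each (Participants and Recruitment), equal numbers in the two orders (Randomisation), and one session of each drink (Procedure).

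**Step 1: what signing after session one reveals to someone who knows the design.**

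| Reading of the rule | Alcohol first | Placebo first | Chance of naming the session-two drink |
|---|---|---|---|
| Alcohol recipients only, at each session | signs, so session two is placebo | does not sign, so session two is alcohol | 0.5 × 1 + 0.5 × 1 = 1.0 |
| Everyone, at each session (Procedure) | signs | signs | 0.5 × 0.5 + 0.5 × 0.5 = 0.5 |
| Everyone, once, after session two | nothing signed yet | nothing signed yet | 0.5 |

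Only the first reading discloses anything. A participant can make the inference only if aware that each person gets each drink once, and the protocol does not state that participants are told this.

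**Step 2: which data are exposed.** In each session the tasks start at minute 40. The questionnaires and BrAC reading follow at minute 65, and signing comes as the participant leaves. Both possible disclosures therefore come after the session-one outcomes, which are unaffected. The upper limit is the session-two visits: 88 of 88 × 2 = 176, of which 88 / 2 = 44 are alcohol and 44 placebo. This assumes that all participants attend both sessions and that the first reading is applied to all of them.

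**Step 3: whether counterbalancing removes the effect.** Suppose knowing the drink shifts a session-two alcohol score by *a* and a session-two placebo score by *p*. Half the participants have alcohol second, and their alcohol-minus-placebo difference moves by *a*. The other half have placebo second, and theirs moves by −*p*. The average shift is (*a* − *p*) / 2. Equal orders cancel a shift common to both drinks (*a* = *p*), but not one that differs by drink. The documents give neither *a* nor *p*, so no size or sign can be put on the result.

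**The case against.** The case for reading the text benignly is substantial.

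- The Safety sentence does not say that *only* alcohol recipients sign, or that they sign at the session where they drank. It calls the document a post-study form, and by the end of the study every completer has had alcohol. The card and the form may also be two different documents.
- The Procedure is the operative section and already gives the safe rule. The offers of a taxi and of staying behind are also made regardless of drink.
- The collaborator who makes the drinks presumably knows them and could handle the form and the BrAC reading.
- Participants are expected to feel some effect at this dose, so some may identify the drink anyway. The computerised forced-choice tasks also leave the tester little room to influence scores.

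All of this stands, and it limits the point. It does not remove it: a form about conduct on the day of drinking is most naturally signed on that day, and the two sections give different rules for who signs.

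Two stronger inferences are tempting. A reader might conclude that testers will certainly be unblinded. The text does not support that, because it does not assign the form or the BrAC reading to the tester. A reader might also conclude that the protocol discloses BrAC values. It does not say so; that part rests on silence about masking, not on a stated unblinding.

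**Conclusion.** The point holds as a minor conflict between two stated rules. If the Safety wording governs after session one, whoever administers the form must know the drink, and the session-two drink is fixed as well. If the Procedure governs, or the form is signed after session two, signing reveals nothing and only the secondary BrAC point remains.

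Exposure is confined to session-two tasks and questionnaires, in at most 88 of 176 visits. A reader might infer that the treatment comparison is biased, or that only session-one data could be trusted. The documents support neither: they show a route by which the blind could fail, not that it fails or that failure would move the results in a known direction or by a known amount. The planned sample size and power are not in question here.

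**What to change.** **Signing.** In the Safety section, replace the conditional sentence with: *All participants will read and sign the safety card before leaving each session.* This matches the Procedure. Compared with signing by alcohol recipients only, it adds at most 88 signatures, one per placebo session. Compared with the Procedure as written, it adds none.

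**BrAC (optional, cheap).** After the mention of the post-task reading in the Procedure, state that the session-one value is kept from the tester and participant until session two is complete, unless it is needed for safety. This could be done with a covered display and a stored value, if the device allows, or by having the collaborator who already makes the drinks handle the reading. The small downside is that the tester does not routinely see the BrAC as the participant leaves. The terms for leaving need not change, because the protocol sets no BrAC value for release.

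Neither change affects sample size, dose, outcomes or analysis.
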